6.2.3.1.1. Criteria for Rechallenge of Givosiran After Being Withheld for ALT Elevation

For patients in whom givosiran dosing is withheld due to elevated ALT, resumption of dosing may be considered using the following guidelines:

- Patients who did not meet criteria for study drug discontinuation per [Table 4](#) may be considered for rechallenge following consultation with the medical monitor and

resolution of ALT to $\leq 2 \times$ ULN or $\leq 2 \times$ baseline (for patients who had elevated baseline ALT)

- The decision to rechallenge the patient should be discussed and agreed upon by the patient, Investigator, and medical monitor
- The dose regimen for patients who meet rechallenge criteria, regardless of their dose at the time of the ALT elevation, is a dose of either 1.25 or 2.5 mg/kg monthly per Investigator judgement and after discussion with the medical monitor:
 - LFTs, INR and TBL will be monitored every 2 weeks (± 7 days) for the first month, then monthly (± 7 days or during the scheduled study visits) as per the Schedule of Assessments
 - Laboratory monitoring and dosing rules in response to LFT elevation will follow [Table 4](#) guidelines
- If dose withholding rules per [Table 4](#) are met on rechallenge with the 1.25-mg/kg dose, permanently discontinue dosing
- If a patient experiences a second dose hold due to LFT elevation while on 2.5 mg/kg monthly:
 - Follow [Table 4](#) guidelines for monitoring and evaluations
 - If ALT resolves to $\leq 2 \times$ ULN, redosing with 1.25 mg/kg monthly may be considered after discussion with the Alnylam medical monitor. If dosing is resumed, follow the guidance above for rechallenge regimen regarding laboratory monitoring and dosing rules. No subsequent re-escalation to 2.5 mg/kg monthly will be allowed.

6.2.3.2. Monitoring and Dosing Rules Based on Lipase and Amylase Results

Lipase and amylase results should be reviewed prior to dosing.

The criteria for withholding, monitoring and stopping study drug dosing based on lipase and amylase results are detailed in [Table 6](#).

Table 6: Monitoring and Dosing Rules in Patients with Lipase or Amylase Elevations	
Hold Further Dosing	
• If a lipase or amylase elevation $>3 \times$ULN (or $3 \times$ baseline in patients with elevated baseline value) occurs, with or without clinical symptoms, until confirmation from the central laboratory (within 2 to 3 days, but no greater than 7 days).• If the elevated lipase/amylase is accompanied by clinical symptoms consistent with pancreatitis (eg, epigastric pain, vomiting), dosing should be held until any additional work-up is complete.

Table 6: Monitoring and Dosing Rules in Patients with Lipase or Amylase Elevations	
	
 • If the elevation of either lipase or amylase is confirmed, an imaging evaluation should be obtained (eg, right upper quadrant ultrasound and/or other testing, based on Investigator judgment). • Monitor lipase/amylase every 2 weeks (± 7 days) until the elevated lipase and/or amylase value declines to $<3 \times \text{ULN}$.
Dosing May Resume	
 • After consultation with the medical monitor and Investigator if the patient is asymptomatic and imaging studies do not reveal hepatobiliary or pancreatic abnormalities. • If an alternate etiology was identified for the elevations and the condition has resolved. • Monitor lipase/amylase every 2 weeks (± 7 days) until the value declines to $<3 \times \text{ULN}$.
Permanently Discontinue Dosing	
 • If the patient is diagnosed with acute pancreatitis with no known alternate etiology (eg, acute gallstones) • If the patient experiences persistent lipase and amylase elevations $>3 \times \text{ULN}$ for >2 months without periods of recovery to $<3 \times \text{ULN}$

Abbreviations: ULN=upper limit of normal

For lipase and amylase testing, local laboratory results may be used to inform dosing decisions; however, parallel samples should be collected for analysis at the central laboratory.

Lipase and amylase testing and imaging evaluations should also be considered at any point in the study if a patient experiences uncharacteristic signs and symptoms during porphyria attacks and there is clinical suspicion of pancreatitis.

6.2.3.3. Monitoring and Dosing Rules in Patients with Potential Cases of Anaphylactic Reaction

An anaphylactic reaction is a severe, potentially fatal, systemic allergic reaction with acute onset (minutes to hours). For reference see Section 11.2 (28).

Stop administering the study medication immediately if an anaphylactic reaction to the study medication is suspected. Study medication must be permanently discontinued in patients for whom an anaphylactic reaction is assessed as related to the study medication.

Laboratory testing: Obtain blood sample for tryptase, total IgE, and ADA antidrug antibodies (ADA) ideally within 15 minutes to 3 hours after the onset of a suspected anaphylactic reaction; however, up to 6 hours is acceptable. An additional blood sample to assess tryptase, total IgE, and ADA should be obtained between 1 to 2 weeks from onset of event. Local laboratory may be used to analyze samples; however, parallel samples should be sent to the central laboratory for analysis. Sample collection and shipping instructions are included in the Laboratory Manual.

Reporting: The PI or designee must notify the sponsor or designee within 24 hours of the occurrence of a suspected case of anaphylactic reaction or being informed of the case as required for AEs of Clinical Interest (AECI) and SAEs, per AE reporting requirements (Section 7.5.6.1 through Section 7.5.6.3).

6.2.3.4. Dose Escalation Guidance for Givosiran from 1.25 mg/kg Once Monthly to 2.5 mg/kg Once Monthly in the Open-Label Period

After implementation of amendment 3 and until implementation of amendment 5, patients assigned to the once monthly 1.25-mg/kg treatment group may be allowed to have their monthly dose increased to 2.5 mg/kg starting at the Month 13 Study Visit (when 6 months of open-label givosiran dosing have been completed at 1.25 mg/kg), based on discussion and agreement by the Investigator and medical monitor. Dose escalation may be considered if the following criteria are met:

- Tolerability to givosiran at 1.25 mg/kg once monthly has been demonstrated based on no dose interruptions due to LFT elevations at the 1.25 mg/kg once monthly dose level (see Section 6.2.3.1) and no significant safety concerns due to other AEs that would preclude a patient from receiving a higher dose of givosiran as judged by the Investigator and Sponsor.
- Urine ALA levels (mmol/mol Cr) are not stably maintained \leq ULN or are inducible
- Patient has inadequate clinical response (eg, breakthrough attacks or ongoing chronic symptoms), according to Investigator judgement.

Upon implementation of amendment 5, all patients receiving 1.25 mg/kg givosiran once monthly who do not have ongoing clinically relevant transaminase elevations will have their dose increased to 2.5 mg/kg givosiran once monthly based on tolerability alone, without any criteria for ALA reduction or clinical activity. Dose increases should take effect as of the date that sufficient study drug material can be made available for the patient.

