evaluation of the PD, efficacy, and safety of the 1.25 mg/kg monthly dose of givosiran, while continuing to provide data on the 2.5 mg/kg monthly dose. Based on the first 6 months of treatment during the OLE period in patients who received placebo in the double-blind period, a trend toward increased benefit, as indicated by greater reductions in composite attacks, hemin use, and ALA and PBG levels, was observed with the 2.5-mg/kg once monthly dose compared to the 1.25-mg/kg once monthly dose. Given the trend toward increased benefit with the 2.5-mg/kg dose of givosiran compared to the 1.25-mg/kg dose and considering that AHP is a disease in which each attack is serious, highly morbid, and carries potential for irreversible neurologic damage, implementation of amendment 5 increases the dose for all patients receiving 1.25 mg/kg givosiran once monthly who do not have ongoing clinically relevant transaminase elevations to the recommended dose of 2.5 mg/kg givosiran SC once monthly, which was approved by the United States FDA in November 2019 and received a CHMP positive opinion in January 2020.

The concentration of givosiran in the liver is the primary driver for its pharmacodynamic effects, which is primarily affected by body weight. Population pharmacokinetic-pharmacodynamic modeling and simulation across different body weights show similar liver exposures of givosiran in adolescents and adults following monthly dosing and consequently similar extent and duration of urinary ALA suppression. Therefore, the same doses are proposed to be administered to both adults and adolescents in this study.

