6.2.2.2. During the Open-Label Extension Period (After Month 6 through End of Treatment)

Patients who crossed over to the OLE period prior to implementation of amendment 3 (ie, under amendment version 1 or 2) and are receiving 2.5 mg/kg once monthly will remain on that dose. Upon entry to the OLE period under amendment version 3, patients will cross over to receive a 1.25 mg/kg once monthly dose of givosiran. After implementation of amendment 3 and until implementation of amendment 5, a dose increase to 2.5 mg/kg once monthly may be permitted starting at Month 13 for patients receiving 1.25 mg/kg once monthly (see Section 6.2.3.4).

Upon implementation of amendment 5, all patients receiving 1.25 mg/kg givosiran once monthly who do not have ongoing clinically relevant transaminase elevations will have their dose increased to 2.5 mg/kg givosiran once monthly per guidance in Section 6.2.3.4.

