6.2.3. Dose Modifications

During the 6-month double-blind treatment period, no study drug dose modifications will be allowed, except in response to LFT elevations as described in Section 6.2.3.1.

During the open-label extension period, dosing modifications will be allowed under the following circumstances:

- In response to LFT elevations as described in Section 6.2.3.1
- After implementation of amendment 3 and until implementation of amendment 5, patients assigned to the once monthly 1.25-mg/kg treatment group who experience inadequate disease control may be allowed to have their monthly dose increased to 2.5 mg/kg starting at Month 13 (when 6 months of open-label givosiran dosing have been completed at 1.25 mg/kg) based on discussion and agreement by the Investigator and medical monitor, demonstration of tolerability givosiran, and fulfillment of ALA and clinical activity criteria as described in Section 6.2.3.4.
- Upon implementation of amendment 5, all patients receiving 1.25 mg/kg givosiran once monthly who do not have ongoing clinically relevant transaminase elevations will have their dose increased to 2.5 mg/kg givosiran once monthly based on tolerability alone, without any criteria for ALA reduction or clinical activity. See Section 6.2.3.4 for further information on dose escalation.

If a study drug-related AE occurs in a patient that the Investigator judges as presenting a potential risk to the patient for further dosing, the study drug dose may be held at the discretion of the Investigator and the medical monitor should be contacted.

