- Additional samples may be collected for assessment of potential alternative causes of liver injury, which may include AAT, ceruloplasmin, acetaminophen/paracetamol levels, anti-LKM antibodies, toxicology screen, ferritin, parvovirus B19, anti-SLA antibodies, gamma-globulins (including IgE and IgG levels), and transferrin saturation, as clinically indicated.

^a HIV testing will not be performed where prohibited by local regulations.

Purpose: Add specific guidance for rechallenge in patients who meet criteria after dose interruption

The primary change occurs in Section 6.2.3.1.1, Criteria for Rechallenge of Givosiran After Being Withheld for ALT Elevation

Added text:

For patients in whom givosiran dosing is withheld due to elevated ALT, resumption of dosing may be considered using the following guidelines:

- **Patients who did not meet criteria for study drug discontinuation per Table 4 may be considered for rechallenge following consultation with the medical monitor and resolution of ALT to $\leq 2x$ ULN or $\leq 2x$ baseline (for patients who had elevated baseline ALT)**
- **The decision to rechallenge the patient should be discussed and agreed upon by the patient, Investigator, and medical monitor**
- **The rechallenge regimen is a reduced dose of 1.25 mg/kg monthly:**
 - LFTs and INR will be monitored every 2 weeks (± 7 days) for the first month, then monthly (± 7 days or during the scheduled study visits) as per the Schedule of Assessments**
 - Laboratory monitoring and dosing rules in response to LFT elevation will follow Table 4 guidelines**
 - If dose withholding rules per Table 4 are met on this dose, permanently discontinue dosing**
- **Dose re-escalation to 2.5 mg/kg monthly may be considered if the following criteria are met:**
 - Approval by the medical monitor after at least 3 doses of 1.25 mg/kg monthly for patients who meet both criteria below:**
 - **Patient has not met dose withholding or discontinuation rules per Table 4 during treatment with 1.25 mg/kg monthly**
 - **Patient has inadequate control of porphyria symptoms on the 1.25 mg/kg monthly regimen, per investigator's assessment**

Added text
(continued):

LFTs and INR will be monitored every 2 weeks (± 7 days) for the first month after dose re-escalation, and then monthly as per the Schedule of Assessments

If a patient experiences a second dose hold due to LFT elevation while on 2.5 mg/kg monthly:

- **Follow Table 4 guidelines for monitoring and evaluations**

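### The Amendment 5 dose-increase rule in Protocol Section 6.2.3.4 makes no exception for patients whom Section 6.2.3.1.1 bars from 2.5 mg/kg after a second liver-test hold (minor safety-text correction)

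*Protocol*

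**What the plan says.** Two operative rules in the current protocol (Amendment 7) govern the move from 1.25 to 2.5 mg/kg in the open-label extension.

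**The increase.** Section 6.2.3.4 sets a rule that applies once Amendment 5 is in force: "all patients receiving 1.25 mg/kg givosiran once monthly who do not have ongoing clinically relevant transaminase elevations will have their dose increased to 2.5" (in mg/kg). The sentence goes on to say that this is "based on tolerability alone, without any criteria for ALA reduction or clinical activity".

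**The bar.** Section 6.2.3.1.1 has a bullet that begins "If a patient experiences a second dose hold due to LFT elevation while on 2.5 mg/kg monthly". Under it, redosing at 1.25 mg/kg may be considered if ALT resolves to 2x ULN or below, after discussion with the medical monitor. It ends: "No subsequent re-escalation to 2.5 mg/kg monthly will be allowed". The bar carries no time limit and no reference to an amendment.

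**How they are joined.** Section 6.2.3 introduces a list with "During the open-label extension period, dosing modifications will be allowed under the following circumstances". Changes made in response to liver tests and the Amendment 5 increase are separate bullets in that list, with no order between them. The increase is repeated in seven other places: the Synopsis (Study Design), Table 3 footnote h, and Sections 1.3, 1.4, 4.1, 6.2.2.2 and 6.2.3. None of these contains an exception for barred patients.

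**The concern.** A patient on 1.25 mg/kg because of two liver-test holds on 2.5 mg/kg appears to meet both rules. One keeps that patient at 1.25 mg/kg and the other moves the patient to 2.5 mg/kg. The increase is worded as a mandatory step for everyone outside a single exclusion, and that exclusion looks at current elevations rather than at history.

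What is at stake is open-label dosing safety. Section 1.4 says that the 1.25 mg/kg dose was introduced because of liver-test elevations, and Section 1.5 lists elevated transaminases among the potential safety concerns. A site that applied Section 6.2.3.4 without consulting Section 6.2.3.1.1 could return a patient to a dose that had already led to two holds.

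**Working it through.** No statistical figure is involved. The check sets the rules side by side and then asks whether a patient could have been in the affected position.

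**1. The same patient under each rule.** Take a patient restarted on 1.25 mg/kg after a second hold on 2.5 mg/kg.

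| Rule | Condition | Met? | Dose |
|---|---|---|---|
| 6.2.3.1.1 | Second liver-test hold while on 2.5 mg/kg | Yes | Stay at 1.25 mg/kg |
| 6.2.3.4 | On 1.25 mg/kg, no ongoing clinically relevant elevation, tolerability | Normally yes on the first two; the third is undefined | 2.5 mg/kg |

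The ratio of the two doses is 2.5 / 1.25 = 2.

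**2. Does the exclusion for ongoing elevations remove the conflict?** Restarting requires ALT at or below 2x ULN. The lowest action band in Table 4 begins above 3x ULN (normal baseline), and the ALT threshold for an adverse event of clinical interest in Section 7.5.6.1 is also above 3x ULN. A patient at the restart level would normally not be regarded as having an ongoing clinically relevant elevation. This is inference: the protocol does not define the term or tie it to Table 4, and ALT could rise again after the restart.

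**3. Does the tolerability qualifier remove it?** It is not defined for the Amendment 5 rule. The only definition in Section 6.2.3.4 belongs to the window between Amendments 3 and 5. Its liver-test limb counts interruptions at the 1.25 mg/kg level only, so two holds at 2.5 mg/kg would not fail it. Its other limb concerns other adverse events, as judged by the investigator and sponsor. Three of the seven repeats (Table 3 footnote h, Sections 1.4 and 6.2.2.2) do not mention tolerability.

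**4. Where the repeats point.** Six of the seven send the reader to Section 6.2.3.4; Section 6.2.2.2, for example, says patients "will have their dose increased to 2.5 mg/kg givosiran once monthly per guidance in Section 6.2.3.4". Section 1.4 alone does not: it says that "implementation of amendment 5 increases the dose for all patients receiving 1.25 mg/kg givosiran once monthly who do not have ongoing clinically relevant transaminase elevations", without a pointer. An exception placed in Section 6.2.3.4 therefore reaches every repeat but one.

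**5. Could such a patient exist when Amendment 5 took effect?** The amendment summaries are used here only as history. The Amendment 2 summary shows a route back to 2.5 mg/kg after a first hold: "Approval by the medical monitor after at least 3 doses of 1.25 mg/kg monthly for patients who meet both criteria below". It also provided for a second hold and a return to 1.25 mg/kg if that dose had been tolerated.

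- Amendment 2 (26 July 2018) to Amendment 5 (12 February 2020): 566 days; 566 / 28 = 20.2 dosing intervals.
- Minimum doses: 1 at 2.5 before the first hold + 3 at 1.25 + 1 at 2.5 before the second hold + 1 back at 1.25 = 6, plus two ALT recoveries.

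There was calendar room, and that is all this shows. Amendment dates are not site implementation dates. The Amendment 6 rationale places elevations mainly 3 to 5 months after starting givosiran, and the route also required inadequate symptom control and the medical monitor's approval.

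**6. Timing of the current text.** Amendment 5 (12 February 2020) to Amendment 7 (29 March 2021) is 411 days, so most of the switching should already have taken place.

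**The case against.** The best answer is that a specific, absolute safety prohibition overrides a general transition rule. Amendment 5 revised both sections together: it edited the second-hold bullet and kept the bar, which suggests the bar was meant to survive. Section 6.2.3 lists what is permitted, and a permissive list does not cancel an express prohibition. This stands as the likely intent. It remains something the investigator must work out, because Section 6.2.3.4 neither says it nor cites Section 6.2.3.1.1.

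The second answer is that a patient with two holds on 2.5 mg/kg could hardly be escalated on tolerability. This stands in part: the qualifier gives an investigator room to withhold the increase. It does not oblige anyone to do so, and the only definition nearby points the other way on liver-test holds.

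Third, other safeguards reduce the risk. Redosing after a second hold needs discussion with the medical monitor, ALT and bilirubin from the preceding 6 weeks must be reviewed before dosing, and a dose may be held for a drug-related event that the investigator judges a risk. These stand and lower the likely harm.

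Fourth, the group may be empty and the switch is largely past. Both points stand and limit the severity.

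A reader might infer more: that the protocol compels a doubled dose in barred patients, or that some received it. The documents support neither. The tolerability wording leaves discretion, and no such patient is reported. Nor does the point extend to patients after a first hold, for whom Section 6.2.3.1.1 allows either dose, or to patients placed on 1.25 mg/kg after Amendment 5.

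**Conclusion.** The conflict is real but narrow. For a patient on 1.25 mg/kg after a second liver-test hold on 2.5 mg/kg when Amendment 5 was implemented, Sections 6.2.3.1.1 and 6.2.3.4 can give doses that differ by a factor of two, and nothing states which governs. The bar is probably intended to prevail.

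This rests on two readings of undefined terms: that ALT at or below 2x ULN is normally not an ongoing clinically relevant elevation, and that tolerability permits but does not require withholding the increase. The number of patients is not given and may be zero.

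Only open-label dosing safety is affected. The primary and secondary analyses use the 6-month double-blind period, which precedes any Amendment 5 switch. Where that switch has been made, an edit now corrects the text and not a past dose. This is a minor safety-text correction.

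**What to change.** Add to the Amendment 5 sentence in Section 6.2.3.4: *except patients barred from re-escalation to 2.5 mg/kg under Section 6.2.3.1.1*. Add a cross-reference to Section 6.2.3.4 in Section 1.4. The other six repeats already point there and need no change.

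The cost is two text edits. No procedure, visit, patient or analysis is added, and the change matches what the sponsor appears to have intended.

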6.2.4. Preparation, Handling, and Storage

Study drug will be stored upright and refrigerated at approximately 2 to 8°C.

Staff at each clinical study center, or the home healthcare professional, will be responsible for preparation of givosiran doses, according to procedures detailed in the Pharmacy Manual. In cases where givosiran is administered at home by a patient/caregiver, dosing may be prepared and administered by the patient/caregiver according to procedures detailed in the Patient/Caregiver Storage and Administration Instructions. No special procedures for the safe handling of study drug are required.

A Sponsor representative or designee will be permitted, upon request, to audit the supplies, storage methods, dispensing procedures, and records.

Additional storage and preparation details are provided in the Pharmacy Manual and the Patient/Caregiver Storage and Administration Instructions.

6.2.5. Packaging and Labeling

All packaging, labeling, and production of study drug will be in compliance with current Good Manufacturing Practice specifications, as well as applicable local regulations. Study drug labels and external packaging will include all appropriate information as per local labeling requirements. Additional details will be available in the Pharmacy Manual.

6.2.6. Accountability

The Investigator or designee will maintain accurate records of receipt and the condition of the study drug supplied for this study, including dates of receipt. In addition, accurate records will be kept of when and how much study drug is dispensed and administered to each patient in the study. Any reasons for departure from the protocol dispensing regimen must also be recorded.

At the completion of the study, there will be a final reconciliation of all study drugs. All used, partially used, and unused study drug will be returned to the Sponsor (or designee) or destroyed at the clinical study center according to applicable regulations.

Further instructions about drug accountability are detailed in the Pharmacy Manual.

